2.2.2 Secondary Objectives

- To assess the cellular immune response of HepTcell in treatment-naïve patients with inactive CHB.
- To assess the safety of HepTcell in treatment-naïve patients with inactive CHB.

2.3 Study Design

This is a Phase 2, randomized, double-blind, placebo-controlled, multicenter clinical trial to evaluate the antiviral effects, immunogenicity, and safety of HepTcell in treatment-naïve patients with inactive CHB and low HBsAg levels (10 to 200 IU/mL).

After providing written informed consent, patients will undergo a screening period of up to 35 days. A Fibroscan will be performed in all patients who have not had this examination within the previous 12 months, except for patients with a prior history of liver biopsy within the past 2 years demonstrating no evidence of significant fibrosis.

Patients who meet inclusion and exclusion criteria will be randomized in a 1:1 ratio to receive 6 IM doses of HepTcell or placebo (normal saline) at study visits 4 weeks apart (Days 1, 29, 57, 85, 113, 141). Randomization may occur up to 3 working days before the first day of dosing to allow for the possible preparation of study medication by a central pharmacy and shipment to the study site. Adverse events (AEs) will be monitored, and blood samples will be collected for quantitative HBsAg (qHBsAg), antibodies to hepatitis B surface antigen (anti-HBs), HBV DNA, HBV pre-genomic RNA (pg-RNA), hepatitis B corerelated antigen (HBcrAg), and interferon gamma (IFN-γ) ELISpot assay in peripheral blood mononuclear cells (PBMCs). Patients will record any reactogenicity events (see section 5.3.3.7) for 7 days after

administration of each dose of study medication. A visit consisting of a targeted physical examination and safety laboratory tests, including liver panels, will be conducted 7±2 days after each administration of study medication. These visits, per the schedule of events (see Protocol), may be conducted at home or workplace or, in part, as a telemedicine visit, at the discretion of the Investigator.

If the patient has experienced an acute illness or temperature > 38°C in the 2 days prior to dosing, the administration of study medication and corresponding visit will be delayed until it has been resolved.

A Safety Committee will conduct regular blinded reviews of all AEs and reactogenicity events. The safety of study participants will also be overseen by an unblinded Data Monitoring Committee (DMC); its responsibilities will be laid out in a DMC charter.

If a patient prematurely discontinues study medication on or before Day 169, the Day 169/Early termination procedures will be performed. Patients who prematurely discontinue study medication will remain in the study for follow-on study assessments.

Patients will be followed for 52 weeks after the last dose of study medication (504 days beyond Day 1 for patients who complete the 24-week Treatment Period). AEs and concomitant medications will be recorded from the signing of informed consent to Day 169, but only MAEs, NCIs, and IMCs, which will be categorized as AEs, will be followed subsequently. Likewise, concomitant medications will be recorded through Day 169, but only immunosuppressive medications, vaccines, and new HBV treatments or medications associated with MAEs, NCIs, SAEs, hepatitis flares, or hepatic injury will be recorded beyond this point. At the end of the clinical trial, the decision about follow-on treatments and medical care will be made by the patient's medical physician or medical team in accordance with the usual standard of care.

Risk-factor analysis and appropriate surveillance for hepatocellular carcinoma (HCC) may be performed at the discretion of the investigator.

Study Schematic

Each patient will participate in the study up to approximately 77 weeks (a 5-week Screening Period, a 24-week Treatment Period, and a 52-week Follow-up Period commencing after the last dose of study medication at Week 20).

2.3.1 Eligibility and Randomization

Following completion of the screening activities, patients who meet the all the inclusion and none of the exclusion criteria will be registered by the Interactive Web Response System. Eligible patients will be randomly assigned in a 1:1 ratio to HepTcell or placebo treatment groups. Randomization will be stratified by study center to minimize imbalances between treatment groups.

The first 12 patients (6 HepTcell, 6 placebo) will form the sentinel cohort. To assure a 1:1 distribution of HepTcell and placebo in the sentinel cohort, randomization in this group will not be stratified.

If none of the Stopping Rules (see section 5.3.6.1) are met in one or more patients in the sentinel cohort, randomization may continue in the expanded study cohort.

The randomization list will be drawn up by an independent statistician.

2.3.2. Eligibility criteria

2.3.2.1 Inclusion Criteria

- 1. Able and willing to provide informed consent
- 2. Men and women 18 to 65 years of age, inclusive
- 3. Body Mass Index (BMI) 18.0 to 34.9 kg/m², inclusive
- 4. Inactive, treatment-naïve CHB with documented HBsAg positivity for at least 12 months before Day 1. (The history of HBsAg positivity may be reduced to 6 months provided HBV anti-core IgM antibodies are negative).
- 5. qHBsAg ≥ 10 IU/mL but ≤ 200 IU/mL in the 12 months prior to screening or from informed consent to randomization
 - If a patient has more than one qHBsAg value within 12 months and prior to randomization, the patient will be deemed eligible if any one measurement is within the eligible range.
- 6. AST, ALT, INR, albumin, total bilirubin (excluding patients with Gilbert Syndrome, who will only be eligible for study participation if total bilirubin is ≤ 3.0 mg/dL) and direct bilirubin within normal limits at screening. Note: ALT and AST elevations up to 1.5 x ULN are allowed if evidence of hepatic steatosis, defined as one of the following criteria: 1) fatty liver on ultrasound, or other imaging modality or Fibroscan controlled attenuation parameter (CAP) ≥ 260 dB/m. To qualify under these conditions, HBV DNA must be <2,000 IU/mL, and there must be no history or signs of liver disease other than fatty liver and HBV.

- 7. Negative drug screen at screening unless prescribed by a medical practitioner for medical use (NB, recreational and prescription cannabis is allowed)
- 8. For women of childbearing potential (women who are not permanently sterile [documented hysterectomy, bilateral tubal ligation, salpingectomy, or oophorectomy] or postmenopausal [12 months with no menses without an alternative medical cause]):
 - a. Negative pregnancy test on Day 1
 - b. Willingness to practice a highly effective method of birth control with low user dependency from screening through one menstrual cycle after the last dose of study medication, which include:
 - i. Abstinence
 - ii. Sex only with persons of the same sex
 - iii. Monogamous relationship with vasectomized partner
 - iv. Intrauterine device
 - v. Combined estrogen and progestogen containing hormonal contraception associated with inhibition of ovulation (oral, intravaginal, transdermal)
 - vi. Progestogen-only hormonal contraception associated with inhibition of ovulation (oral, injectable or implantable)

vii. Intrauterine hormone-releasing system

Patients who practice true abstinence or who exclusively have same sex partners need not use contraception, provided it is in line with their preferred and usual lifestyle. Periodic abstinence (eg, calendar, ovulation, symptothermal, post-ovulation methods) and withdrawal are not acceptable methods of contraception. Should any such patient stop practicing abstinence, they must use contraception as described above.

- 9. For men with sexual partners of childbearing potential, as defined above:
 - a. Abstinence
 - b. History of vasectomy or surgical sterilization
 - c. Monogamous relationship with a postmenopausal or surgically sterilized partner
 - d. Willingness to practice a highly effective method of contraception, as defined above, for 90 days after the last dose of study medication and to refrain from sperm donation for this time

The same criteria pertaining to abstinence and withdrawal methods in women of childbearing potential (Inclusion Criterion 8) apply to men with sexual partners of childbearing potential

10. Willingness to comply with all aspects of the study through the entire study period

Patients who fail to meet Inclusion Criteria 5 and/or 6 and otherwise meet the requirements for study participation will be permitted one additional blood draw during the same screening period to requalify. Patients who screen fail for other Inclusion Criteria may undergo rescreening at the discretion of the Investigator and Medical Monitor.

2.3.2.2 Exclusion Criteria

Patients who do not meet any of the following exclusion criteria may be included in the study.

- 1. Pregnant or lactating women
- 2. Positive hepatitis B e antigen (HBeAg) at screening
- 3. History of a hepatitis B flare or 1-log increase in HBV DNA or HBsAg in the prior 6 months
- 4. Prior or current history of active or untreated human immunodeficiency virus (HIV), hepatitis C virus (HCV), or hepatitis delta virus (HDV)
- 5. Acute COVID-19, a positive test result for SARS-CoV2 infection, or exposure within 14 days to an individual with acute COVID-19
- 6. Febrile illness (temperature ≥ 38.0 °C) within the past 14 days
- 7. Prior or current history of any underlying liver disease not related to HBV (NB, steatosis, as documented by imaging or Fibroscan CAP, is permitted if ALT and AST are <1.5 x ULN and HBV DNA <2,000 IU/mL and there is no history or signs of liver disease other than fatty liver and HBV)
- 8. Fibroscan > 8.5 kPA at screening, or history of hepatic fibrosis or cirrhosis (NB, a Fibroscan is not required if an examination is performed within 12 months before screening, or a liver biopsy was performed within 2 years before screening and no fibrosis [F1 or greater] was identified.)
- 9. History of cirrhosis or signs of hepatic decompensation, including but not limited to variceal bleeding, ascites, or hepatic encephalopathy
- 10. White blood cell count < 3,500/ μ L, neutrophils < 1,000/ μ L, hemoglobin < 11 g/dL, or platelets < 125,000/ μ L

Note: Individuals of African descent with a white blood cell count <3,500/ μ L will not be excluded for this reason if white blood cell count is \geq 2,500/ μ L, provided that the neutrophil count is \geq 1,000/ μ L and there is no other identified cause of leukopenia.

11. Prior treatment with an approved or investigational agent for HBV.

- 12. History of conditions associated with immunocompromise
- 13. History of conditions associated with altered immune response, such as anaphylaxis, angioedema, or autoimmune disease
- 14. Treatments known to affect the immune system, such as corticosteroids (other than topical or inhaled preparations), alkylating drugs, antimetabolites, cytotoxic drugs, radiation, immune-modulating biologics, allergy injections, immunoglobulins, interferons or other immunomodulating therapies, within 30 days of screening
- 15. Uncontrolled diabetes mellitus, defined as Hemoglobin A₁C (HbA₁C) ≥ 10% at screening
- 16. Receipt of live-attenuated replicating vaccines within 30 days or receipt of any other licensed or authorized vaccines (including vaccines intended to prevent COVID-19) within 14 days prior to Day 1
- 17. Change in any chronically administered medication or treatment within 14 days of screening or inability to maintain these medications at the same dose through Day 169 (NB, patients chronically using aspirin, non-steroidal anti-inflammatory agents, antacids, vitamins, probiotics, and over-the-counter medications will maintain their level of intake throughout the study)
- 18. Malignancy within 3 years of screening, excluding non-melanoma skin cancers and carcinoma *in situ* cervical cancer (NB, patients who have undergone prior screening for HCC by imaging or alpha-fetoprotein levels will have negative test results)
- 19. Untreated alcohol or drug abuse
- 20. Planned elective surgery or hospitalization during the study period
- 21. Participation in a prior trial involving HepTcell or FP-02.2
- 22. Known allergy to any of the ingredients in HepTcell
- 23. Receipt of any investigational drug or treatment within 30 days before Day 1 or planned use during the study period
- 24. Any medical, psychiatric, or social condition or occupational or other responsibility that in the judgment of the Investigator would interfere with or serve as a contraindication to protocol adherence, assessment of safety (including reactogenicity), or a patient's ability to give informed consent

Patients who are excluded by Exclusion Criterion 10 but otherwise meet the requirements for study participation will be permitted one additional blood draw to requalify. Patients who screen fail for other Exclusion Criteria may undergo rescreening at the discretion of the Investigator and Medical Monitor.

2.3.2 Withdrawals

Patients can choose to discontinue study medication or participation in the study at any time, for any reason, without prejudice to their future medical care. Patients could be discontinued for any of the following reasons:

- Patient request/withdrawal of consent
- Noncompliance with study requirements
- Loss to follow-up
- Investigator discretion
- Sponsor request, including termination of the study by the Sponsor

In case of worsening or disease progression, study medication will be discontinued, and the medications prohibited (described in the protocol) will be allowed, at the discretion of the investigator and Sponsor, if it is in the patient's best interest to initiate any treatment prohibited in the study.

If a patient prematurely discontinues study medication before Day 169, Day 169/ET procedures will be performed. Patients who prematurely discontinue study medication will remain in the study for Follow-up Period study assessments, with the dates of visits adjusted to correspond to 13, 26, 39 and 52 weeks after the last dose of study medication.

2.3.3 Study treatment

HepTcell or normal saline placebo will be administered by IM injection at intervals of 4 weeks for 6 doses. Doses will be administered on Days 1, 29, 57, 85, 113, and 141 (±2 days for each dose). All study administration data collected at patient level will be presented in patient level listings as well as by visit. This will include missed doses or dose delays information.

If an authorized COVID-19 vaccine has been administered in proximity to a scheduled IP administration, a ±3-day window is allowed for IP dosing. Also, from the second dose, if the patient has experienced an acute illness or temperature > 38°C in the 2 days prior to dosing, the administration of study medication and corresponding visit will be delayed until the illness or fever has resolved.

2.3.4 Replacement of Patients

Eligible patients who are randomized and withdrawn before their second dose of study medication will be replaced. Patients who have received two doses of study medication who are subsequently withdrawn from the study will not be replaced.

In consultation with the DMC, patients in the Sentinel Cohort may be replaced at any time to assure that the reliability and integrity of the data from this cohort remains intact.

3. STUDY(ANALYSIS) POPULATIONS

3.1 Modified Intent-to-treat population (mITT)

The modified Intent-to-Treat (mITT) population includes all randomized patients who receive any amount of study medication, have a baseline and at least one post-baseline efficacy assessment (i.e., at least one post-baseline measurement for one of the following parameters: qHBsAg, HBV DNA, HBcrAg and pg-RNA).

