6.2. Randomization

Following completion of the Screening activities, patients who meet the all the inclusion and none of the exclusion criteria will be registered by the Interactive Web Response System (IWRS). Eligible patients will be randomly assigned in a 1:1 ratio to HepTcell or placebo treatment groups. Randomization will be stratified by study center to minimize imbalances between treatment groups.

The first 12 patients (6 HepTcell, 6 placebo) will form the sentinel cohort. To assure a 1:1 distribution of HepTcell and placebo in the sentinel cohort, randomization in this group will not be stratified.

If none of the Stopping Rules (see Section 7.1.1) are met in one or more patients in the sentinel cohort, randomization may continue in the expanded study cohort.

The randomization list will be drawn up by an independent statistician.

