10.2. Sample Size

A study of IFN-α2 in a population with inactive CHB reported a mean incremental decrease of 1.3 log-qHBsAg at 24 weeks in those patients completing IFN-α2 treatment compared to non-treatment. Mean decrease would translate to approximately 50% of patients completing treatment achieving 1.3 log-qHBsAg response (reduction). To estimate treatment effect in the current study, the proportion of patients achieving a 1.0-log reduction in qHBsAg is estimated as one-half (25% of patients) who achieve this response. Assuming a response rate of 3% on placebo and 25% on HepTcell, 40 patients will be randomized per treatment group to detect a difference in the proportion of patients treated with HepTcell achieving the primary endpoint compared to patient treated with placebo at a 0.05 level of significance (two-sided) with approximately 80% power.

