10.3. Analysis Sets

Safety Analysis Set: All patients who receive any study medication. Patients will be analyzed according to the treatment that they receive.

Modified intent to treat (mITT) Analysis Set: All randomized patients who receive any amount of study medication, have a baseline and at least one post-baseline efficacy assessment. Patients will be analyzed according to the treatment that they receive. This analysis set will be used for primary and secondary analyses.

Per Protocol (PP) Set: All randomized patients who receive the full designated amount of study medication according to the correct treatment assignment and who have results from HBV serology and viral markers at Day 85.

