10.4. Statistical Methods

10.4.1. Primary Efficacy Endpoint

For the primary analysis, proportions of patients with virologic response, defined as a 1.0-log reduction in HBsAg or serologic clearance of HBsAg, will be compared between HepTcell and placebo groups using Fisher's Exact Test at a 0.05% two-sided level of significance.

Patients who discontinue prematurely or have missing data will be considered nonresponders for that endpoint. Linear and logistic regression will be employed to examine the effects of baseline factors, such as qHBsAg level, HBV DNA levels, and hepatitis B genotype on response.

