5.3 Summary of Statistical Methods

This study is designed as a phase 2 study, exploratory in nature, to evaluate the response to HepTcell in treatment-naïve patients with inactive CHB. Comparisons will be performed between HepTcell and Placebo at a two-sided type I error rate of 0.05 which will not be adjusted for multiple testing.

The study will be considered to have achieved proof-of-concept when the 2-sided p-value is <0.05. Accordingly, the primary and key secondary efficacy endpoints will present 2-sided 95% Confidence Intervals (95%Cls) when applicable.

Unless otherwise specified, efficacy analyses will be performed using the mITT population, where patients will be in the treatment arm to which they received. As described in more detail elsewhere, patients will be analysed according to the treatment of the most treatment received. Moreover, supportive efficacy analyses will be performed in the PP population. Safety related analyses will use the safety population, where patients will be analyzed according to the treatment that they receive.

All applicable baseline data will be summarized by treatment arm (HepTcell, placebo), unless specified otherwise. Safety and efficacy data will also be summarized by treatment arm and additionally by time-point of assessment and/or follow-up, when appropriate.

Continuous variables will be summarized using the number of observations (n), mean (95%CI, if appropriate), standard deviation (SD), Standard error (SE, if appropriate), median, first quartile (Q1), third quartile (Q3), minimum, and maximum along with the total number of patients contributing values.

Descriptive statistics for categorical/qualitative data will include frequency counts and percentages. The denominator for all percentages will be the total number of patients in the treatment arm and dose number (if applicable) within the population of interest, unless stated otherwise in the table footnote.

Change from baseline is calculated only for patients with non-missing values for both the baseline and the time-point of interest and will be missing otherwise.

Statistical comparisons will be performed between HepTcell and placebo at a 5% confidence level.

All relevant patient data will be included in listings. All patients entered into the database will be included in patient data listings. The listings will be generally sorted by treatment arm and then Patient ID, unless specified otherwise.

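### The primary analysis set drops treated patients who have no post-baseline HBV sample, whom the primary rule would score as non-responders, and groups efficacy by treatment received

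*SAP*

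**What the plan says.** - **Primary set.** SAP 3.1 defines mITT as "all randomized patients who receive any amount of study medication, have a baseline and at least one post-baseline efficacy assessment". It lists the qualifying markers as qHBsAg, HBV DNA, HBcrAg and pg-RNA, any one of which suffices. Protocol 10.3 has the same inclusion condition, and SAP 5.3.2 runs the efficacy analyses on mITT.
- **Missing data.** Protocol 10.4.1: "Patients who discontinue prematurely or have missing data will be considered nonresponders for that endpoint". SAP 5.3.2.1 keeps this, except that a patient whose last value before Day 169 was a response counts as a responder. Neither text exempts patients with no post-baseline value.
- **Sampling.** Protocol Table 1 places HBV markers at Screening, Day 1, Day 85 and Day 169 or ET. Table 2 adds Days 323 and 505. Three doses (Days 1, 29 and 57) come before the Day 85 visit.
- **Replacement.** SAP 2.3.4: "Eligible patients who are randomized and withdrawn before their second dose of study medication will be replaced".
- **Grouping.** Protocol 10.3 says of mITT: "Patients will be analyzed according to the treatment that they receive. This analysis set will be used for primary and secondary analyses". SAP 5.3 adds that "patients will be analysed according to the treatment of the most treatment received" and points to a fuller description elsewhere. The SAP contains none.

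**The concern.** The set and the missing-data rule pull in different directions. Under the rule, a treated patient lost in the first 12 weeks is a non-responder. Under the set definition, the same patient is not analysed if no post-baseline marker was ever drawn. Whether a patient is included then depends on something that happens after randomisation and dosing, when one arm is receiving an adjuvanted injection and the other saline. Removing non-responders can only raise an arm's observed rate, so unequal losses would bias the comparison towards the arm that loses more.

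Grouping by treatment received is a second departure from the randomised comparison. It matters only if a patient is mis-dosed. The majority-of-doses rule then gives no arm for an equal split of doses.

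At stake are the reported response rates and, for results close to the line, the SAP's proof-of-concept criterion of a two-sided p below 0.05.

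**Working it through.** **Inputs.** Protocol 10.2: "Assuming a response rate of 3% on placebo and 25% on HepTcell, 40 patients will be randomized per treatment group", tested "at a 0.05 level of significance (two-sided) with approximately 80% power". Allocation is 1:1 (protocol 6.2). The significance level used here is 0.05; the 0.05% printed in protocol 10.4.1 and SAP 5.3.2.1 conflicts with it. The documents give no dropout rate, so *k*, the number of patients per arm with no post-baseline HBV sample, is assumed to range from 0 to 6.

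**Step 1: the plan's own figure.** Exact enumeration of Fisher's test at 40 per arm, 3% vs 25%, gives 78.0% power. The pooled normal formula needs 38 per arm. The stated figure of about 80% with 40 per arm reproduces.

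**Step 2: equal losses and power.** Excluding *k* per arm leaves 40 − k patients at 3% and 25%. Counting them as non-responders keeps 40 per arm and multiplies both rates by (40 − k)/40. Fisher power:

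| k per arm | excluded | counted as non-responders |
|---|---|---|
| 0 | 78.0% | 78.0% |
| 1 | 76.4% | 76.3% |
| 2 | 74.6% | 74.4% |
| 4 | 70.6% | 70.4% |
| 6 | 66.2% | 65.9% |

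With equal losses the two treatments of these patients differ by at most 0.4 points of power. The effect lies in the rates and in unequal losses.

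**Step 3: effect on the rate.** Take 10 responders among 40 treated, with *k* of the non-responders unsampled. The reported rate is 10/(40 − k): 25.0% for k = 0, 25.6% for 1, 26.3% for 2 and 27.8% for 4.

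**Step 4: which test.** Protocol 10.4.1 names Fisher. SAP 5.3.2.1 uses Fisher only if at least 80% of cells have expected counts below 5. In a 2×2 table three cells are 75%, so all four are needed, and the total would have to be below 4 × 5 = 20. With about 80 patients the SAP's rule selects chi-square.

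**Step 5: unequal losses, chi-square without continuity correction.** With *a* of *n* responders on HepTcell and *c* of *m* on placebo, and b = n − a, d = m − c, N = n + m:

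X² = N(ad − bc)² / [n·m·(a + c)·(b + d)]

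- 9/40 vs 3/40: 80 × (9×37 − 31×3)² / (40×40×12×68) = 80 × 240² / 1,305,600 = 3.529, p = 0.060.
- Two unsampled HepTcell patients excluded, 9/38 vs 3/40: 78 × (9×37 − 29×3)² / (38×40×12×66) = 78 × 246² / 1,203,840 = 3.921, p = 0.048.

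Fisher does not cross for this pair (0.115 and 0.063).

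**Step 6: unequal losses, Fisher.** 7/40 vs 1/40 gives p = 0.057. Excluding one HepTcell patient, 7/39 vs 1/40, gives p = 0.029. Much of that jump is the discreteness of the two-sided exact test: chi-square on the same tables gives 0.025 and 0.023, already below 0.05 both times.

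**Step 7: regrouping by treatment received.** Suppose one placebo-randomised responder is counted under HepTcell.

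- 8/40 vs 3/40: X² = 80 × 200² / (40×40×11×69) = 2.635, p = 0.105.
- 9/41 vs 2/39: X² = 80 × 269² / (41×39×11×69) = 4.770, p = 0.029.

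Fisher gives 0.193 and 0.048, so both tests cross here.

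**Step 8: away from the threshold.** 10/40 vs 1/40 has Fisher p = 0.007. With four HepTcell exclusions, 10/36 vs 1/40 has p = 0.002. The conclusion is the same.

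**The case against.** The strongest counter-argument is that the plan already captures most early stoppers. A reader might infer that patients who find the vaccine intolerable simply vanish from the analysis. The documents do not support that. Protocol 7.1 and the Table 1 footnotes give patients who stop study medication the Day 169/ET procedures, which include HBV markers, and keep them in follow-up. One post-baseline marker holds them in mITT, as non-responders unless their last value before Day 169 was a response. Only patients with no ET or later sample are lost. Differential loss is also an assumption: protocol 1.3 reports Phase 1 adverse-event and injection-reaction rates similar to placebo. This stands, and it makes the affected group small.

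A reader might also infer that replaced patients are taken out of mITT. Nothing says so. A replaced patient leaves only if unsampled, like anyone else. What is missing is a statement of how replaced patients are analysed.

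The missing-data rule can be read as operating within mITT, so that there is no contradiction. That reading is natural, but neither document states it. Even so, the post-randomisation exclusion remains, and the only supportive set (Per Protocol) is narrower.

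Finally, no dosing error is documented, the SAP calls the study exploratory, and exclusions are to be listed with reasons (SAP 5.2.1). These points limit the consequence. They do not justify the set.

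**Conclusion.** The point holds in a limited form. The primary set excludes treated patients with no post-baseline HBV marker, whom the stated rule would score as non-responders, and it groups efficacy patients by treatment received. The result is an upward shift in the rate of whichever arm has more unsampled losses: 0.6 points for one such patient and 2.8 points for four, starting from 10/40. Significance changes only when the result is already near 0.05, and which tables cross depends on whether chi-square or Fisher is used. The counts are illustrations; the true number of such patients, their split by arm and any mis-dosing are not in the documents.

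It would be tempting to say that this choice could still decide the proof-of-concept result. The documents do not support that: SAP section 2 and the SAP addendum report that the Week 24 primary and secondary endpoints were not met and that the study is being terminated. What remains at stake is accurate denominators and response rates in the report.

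**What to change.** In protocol 10.3 and SAP 3.1 and 5.3:

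1. Define the primary efficacy set as all randomised patients who received at least one dose, analysed in the arm to which they were randomised.
2. Score patients with no post-baseline HBsAg as non-responders.
3. State that replaced patients stay in the set alongside their replacements.
4. Use treatment received for the Safety set only.
5. Keep the current mITT as a sensitivity analysis.

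Because the Week 24 results are already known, report the new set next to the existing mITT result and label it as a change made after unblinding. The cost is wording and one further run of the primary tables. No new data are needed. The reported response rate may be slightly lower.
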